The ORR will be compared between the treatment arms over the control arm using a one sided Cochran-Mantel-Haenszel (CMH) test, stratified by randomization stratification factors. Odds ratios will be presented with 95% CIs.

Best Overall Response Rate (BRR)

The number and percentage of subjects will be presented for each response category by treatment arm.

Complete Response Rate (CRR)

The same methodology as for analysis of objective response will be applied to complete response rate.

Corticosteroid Use

Systemic corticosteroids that were given orally or by injection, reported either in prior/concomitant medication form until 35 days after the last study drug (ABT-414/TMZ/lomustine) or tumor assessment form will be summarized. Baseline steroid use is defined as any use of systemic steroid prior to and within 14 days of randomization. Post-baseline steroid use is defined as any use of systemic steroid on or after randomization. Steroid dose will be converted to a dexamethasone equivalent dose.³

Table 3. Conversion Factor to Dexamethasone Equivalent Dose

Corticosteroids (mg)	Conversion Factor*
Cortisone	0.75/25
Hydrocortisone	0.75/20
Prednisone, Prednisolone	0.75/5
Methylprednisolone, Triamcinolone	0.75/4
Betamethasone	0.75/0.6

* Dexamethasone equivalent dose (mg) = Conversion factor x Corticosteroid dose (mg).

Baseline steroid dose is defined as the average dose prior to and within 14 days of randomization, i.e., sum of daily doses divided by the number of days treated with steroids. The following summary will be presented for each treatment arm:

- The number and percentage of subjects who are treated with steroids at baseline (yes; no; missing) and post-baseline (yes; no; missing) in a two-way table.
- For subjects with no steroids at baseline and at least one steroid at post-baseline, simple summary statistics for time (in weeks) to steroid use during the study since randomization.
- The number and percentage of subjects who are treated with average steroid dose group (mg/day) at baseline (≤ 2 ; > 2 to ≤ 4 ; > 4 to ≤ 6 ; > 6 to ≤ 8 ; > 8 to ≤ 20 ; > 20 mg/day).
- The number and percentage of subjects with objective response (CR and PR assessed by IRC per RANO criteria) and Kaplan-Meier estimates of PFS, by baseline steroid use status (yes; no; missing), respectively.

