In addition, steroid dose change (sustained reduction and complete reduction) relative to baseline will be summarized. Sustained reduction of steroid dose is defined as 50% or more steroid dose reduction, relative to baseline, for 50% or more of the time on study drug (ABT-414/TMZ/lomustine). Complete reduction is defined as discontinuation of steroid use for $\geq 25\%$ of the time on study drug (ABT-414/TMZ/lomustine).

- The number and percentage of subjects with objective response status (responders; non-responders) and Kaplan-Meier estimates of PFS for subjects who have sustained steroid reduction and for subjects who have complete steroid reduction, respectively.

Quality of Life

Subject self-reported health related quality of life (HRQoL) outcomes are assessed at the baseline, Week 8 MRI visit (while on-treatment), Week 16 MRI visit (while on-treatment), and Month 6 visit (any time during the 6th and 7th month after the date of

randomization regardless of treatment or progression status) by using the QLQ-C30 version 3 (Table 4) and QLQ-BN20 (Table 5).

The main objective of HRQoL assessment is to determine the impact of ABT-414 on overall global health and HRQoL. A secondary objective is to evaluate the effect of the treatment on the remaining symptoms and functioning scales as treatment-related side effects may have a (temporary) negative influence on the health related domains of HRQoL of these subjects. The QLQ (quality of life questionnaire) comprises distinct scales, each of which represents a different aspect of QoL, and the individual questions on the QLQ are called items.

The QLQ-C30 is composed of global health status/QoL scale; five functional scales (physical, role, emotional, cognitive, and social); three symptom scales (fatigue, nausea and vomiting, and pain); and six single items (dyspnea, insomnia, appetite loss, constipation, diarrhea, and financial difficulties).

Table 4. Scoring the QLQ-C30

QLQ-C30	Item (Question) Numbers	Item Range*
Global health status/QoL		
Global health status/QoL	29, 30	6
Functional scales		
Physical functioning	1, 2, 3, 4, 5	3
Role functioning	6, 7	3
Emotional functioning	21, 22, 23, 24	3
Cognitive functioning	20, 25	3
Social functioning	26, 27	3
Symptom scales/Items		
Fatigue	10, 12, 18	3
Nausea and vomiting	14, 15	3
Pain	9, 19	3
Dyspnea	8	3
Insomnia	11	3
Appetite loss	13	3
Constipation	16	3
Diarrhea	17	3
Financial difficulties	28	

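### Two exploratory steroid summaries in SAP 10.3 select patients on post-randomization follow-up: time to steroid use mixes the steroid effect with the PFS effect, and PFS in steroid reducers carries immortal-time bias

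*SAP*

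**What the plan says.** All of this is in SAP 10.3, Corticosteroid Use, unless stated otherwise.

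- Time to steroid use, by arm: "For subjects with no steroids at baseline and at least one steroid at post-baseline, simple summary statistics for time (in weeks) to steroid use". No censored estimate is named for subjects who never start.
- In the same list, a two-way table: "The number and percentage of subjects who are treated with steroids at baseline (yes; no; missing) and post-baseline (yes; no; missing".
- Data window: steroids on the medication form "until 35 days after the last study drug (ABT-414/TMZ/lomustine) or tumor assessment form will be summarized".
- Sustained reduction is "50% or more steroid dose reduction, relative to baseline, for 50% or more of the time on study drug (ABT-414/TMZ/lomustine". For the other group, "Complete reduction is defined as discontinuation of steroid use for" at least 25% of the time on study drug.
- For these groups the SAP gives objective response status and "Kaplan-Meier estimates of PFS for subjects who have sustained steroid reduction and for subjects who have complete steroid reduction, respectively". It names no landmark, time-dependent handling, non-reducer curve, hazard ratio or test.

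SAP 10.1 sets the general rule that subjects without the event are right-censored. Protocol 5.4 stops study treatment at progression, and Protocol 6.4.1 continues scheduled MRI only until progression. SAP 4.1 names steroid use against control among the trial's objectives. SAP 10.2 lists it as an exploratory endpoint.

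**The concern.** Time to first steroid use is a censored outcome. A summary in starters alone reports only the times that fit inside each subject's observation window, and that window largely follows PFS. The result is too short, and it differs between arms whenever PFS differs, whatever the drug does to steroid need.

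Reduction status is a share of total time on drug, so it is known only at the end of treatment. A subject who progresses early has little time to reach the reduction and hold it long enough. The reducer groups are therefore partly selected for long PFS, yet their PFS is counted from randomization.

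At stake is how far these outputs can inform the steroid objective. No primary or tested secondary result depends on them.

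**Working it through.** **Plan inputs.** Median PFS is 2.6 months (control) and 4.8 months (ABT-414), SAP 4.4; 2.6/4.8 = 0.542, matching the stated HR of 0.54. Window: 35 days after last drug. Month: 30.4375 days (SAP 6.0), so d = 35/30.4375 = 1.150 months and one month is 4.348 weeks. The documents give no figure for the steroid analyses.

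**Assumptions not in the documents.** Exponential times; time on drug equals PFS; steroid start and steroid reduction independent of PFS; steroid start rate λ = 0.05 to 0.3 per month; median time to reduction 1 to 3 months; a reduction, once reached, is kept.

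**(a) Time to steroid use in starters.** Let μ = ln2/(median PFS), with observation to PFS + d.

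- Share who start: P = 1 − e^(−λd) · μ/(μ+λ)
- Mean time in starters: { [1 − e^(−λd)(1+λd)]/λ + λe^(−λd)[d/(λ+μ) + 1/(λ+μ)²] } / P

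The start rate is the same in both arms (control vs ABT-414):

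| λ per month | Starting | Mean in starters, weeks | True mean 1/λ, weeks |
|---|---|---|---|
| 0.05 | 20% vs 30% | 14.3 vs 22.7 | 87 |
| 0.1 | 35% vs 47% | 12.4 vs 18.1 | 43 |
| 0.2 | 55% vs 67% | 9.8 vs 12.9 | 22 |
| 0.3 | 67% vs 77% | 8.2 vs 10.1 | 14 |

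Three further checks:

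- *Equal PFS and equal start rate.* Both arms use the same μ and λ, so the expected difference is zero. Simulated trials with 40 per arm (assumed) gave a mean difference in medians of −0.01 to 0.07 weeks.
- *Higher start rate with ABT-414.* At 0.15 against 0.1 in control, starters' means are 15.1 vs 12.4 weeks, so the arm with more frequent starts still looks later.
- *True halving of the start rate, PFS median 2.6 months in both arms.* True median starts are 17.4 vs 34.8 weeks (4 vs 8 months). The starters' median t solves 1 − e^(−λd) + [λe^(−λd)/(λ+μ)](1 − e^(−(λ+μ)(t−d))) = P/2, giving about 7.5 vs 9.2 weeks. Most of the real effect is hidden.

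**(b) PFS in reducers.** Let ν = ln2/(median time to reduction). A subject is a sustained reducer if reduction comes within half of T (PFS), so k = 0.5ν, and a complete reducer if it comes within three quarters of T, so k = 0.75ν.

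- PFS in reducers: P(T>t) = [(μ+k)e^(−μt) − μe^(−(μ+k)t)]/k

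| Median PFS, all | Median time to reduction 1 / 2 / 3 months: sustained | Complete |
|---|---|---|
| 4.8 months | 7.0 / 8.2 / 8.9 | 6.4 / 7.5 / 8.2 |
| 2.6 months | 4.4 / 5.0 / 5.3 | 4.0 / 4.6 / 5.0 |

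No link between reduction and PFS was put in. If reduction status is settled at randomization, the simulated HR between groups is 1.00.

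**Landmark.** Eight weeks is 56/30.4375 = 1.84 months. Progressed or dead by then: 1 − 2^(−1.84/2.6) = 39% in control and 1 − 2^(−1.84/4.8) = 23% with ABT-414. With status fixed at week 8, the simulated HR is 0.99 to 1.01 for median reduction times of 0.5 to 4 months.

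**The case against.** Much of the case for leaving the text alone is fair.

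- *A reader might infer that both outputs show large differences when nothing differs between arms.* For time to steroid use that is wrong: with equal PFS and observation time the arms agree. The gap needs a difference in PFS or observation time.
- *A reader might infer that the report would show a clean false benefit on steroids.* It would not. The two-way table sits in the same list and, at one common start rate, shows more ABT-414 patients starting (47% vs 35% at 0.1). The damage is that one output suggests more steroid use and the other later use, and neither shows that the rate is the same.
- *Independence from PFS is an assumption.* Protocol 7.1.1.4 can date progression to a steroid increase, and Protocol 7.1.3.4 counts starting steroids for neurological symptoms as clinical progression. If starts cluster at progression, the gap in (a) that is unrelated to steroid need is smaller.
- *A reader might set reducers against non-reducers.* In the model at 4.8 months that gives 7.0 to 8.9 against 1.4 to 2.7 months, an apparent HR of about 0.16 to 0.30. The SAP plans no such curve, HR or test, so this contrast is one a reader would draw. The SAP's PFS curve by baseline steroid use, which conditions only on a baseline factor and is sound, makes it easy to set reducers beside all baseline users.
- *The bias in (b) depends on when reduction happens.* Protocol 3.2 requires a stable or decreasing dose before the baseline MRI, so some reductions may be under way at entry. If status is settled then, the bias is nil.
- *Response by reduction status might be called circular throughout.* Under Protocol 7.1.1.4 only CR requires being off steroids (or on physiologic replacement). PR requires a dose no higher than at baseline.

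What stands is that both outputs select on follow-up and that the starters-only summary departs from the SAP's own censoring rule. The low stakes also stand.

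**Conclusion.** The point holds as a minor one. Starters-only time to steroid use understates the time and cannot separate a steroid effect from a PFS effect. Under the plan's PFS medians and one common start rate, the starters' mean is 14.3 vs 22.7 weeks at 0.05 per month, narrowing to 8.2 vs 10.1 at 0.3. PFS from randomization in reducers is inflated by immortal time: medians of about 7.0 to 8.9 months (sustained) and 6.4 to 8.2 months (complete) against 4.8 overall, with no true link.

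These sizes rest on exponential times, independence from PFS, and assumed start rates and reduction times. They shrink if starts cluster at progression (a) or reductions come early (b). The analyses are exploratory, descriptive and outside the fixed testing sequence, so no conclusion on OS, PFS or ORR is affected.

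**What to change.** 1. Replace the starters-only summary with a Kaplan-Meier or cumulative incidence estimate (death competing) of time to first steroid use, by arm, in all subjects without baseline steroids, censored at the end of steroid data collection. State that this censoring may be informative if steroid use tracks progression. Keep the two-way table.
2. Present PFS by reduction status from a week-8 landmark: classify subjects who are alive and progression-free then, using steroid data up to that date, and start the curves there. Alternatively, enter reduction as a time-dependent covariate. Keep the result descriptive: in small simulated samples (40 baseline steroid users) a landmark log-rank test rejected 7% to 9% of the time with no effect.
3. Note beside the response table that CR by definition requires being off steroids.

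The cost is SAP wording and a small programming change, with no new data. At the plan's medians the landmark leaves out about 39% of control and 23% of ABT-414 patients, which is unequal by arm and should be stated. Week 8 is also the first scheduled MRI, with a window of ±7 days (Protocol 6.3.6), so scan timing partly decides who counts as progression-free.

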6.2 Before randomization

All pretreatment evaluations should be performed within 2 weeks before randomization.

The baseline evaluations include:

- Histologically confirmed *de novo* (primary) glioblastoma with unequivocal first progression after RT concurrent/adjuvant TMZ chemotherapy either at least 3 months after the end of radiotherapy or have tumor progression that is clearly outside the radiation field or have tumor progression unequivocally proven by surgery/biopsy
- Informed consent and consent for future studies
- Demographics (height, weight, race, ethnicity)
- Complete medical history, including documentation of any clinically significant medical condition
- Prior anti-cancer therapy (including start and end dates for prior TMZ chemotherapy and RT)
- Physical examination including, but not limited to, WHO performance status and neurological evaluation
- Ocular examination by an ophthalmologist
- Vital signs (blood pressure, pulse rate and body temperature)
- Quality of life assessment, including EORTC QLQ-C30 and EORTC-BN20 (see section [10.1](#))
- 12-lead ECG
- ◆ Concomitant medications
- ◆ Steroid intake
- Assessment of all adverse events according to CTCAE 4.0
- Hematology (WBC, absolute neutrophil count, lymphocytes, hematocrit, hemoglobin and platelet count)
- Biochemistry (serum creatinine, total bilirubin, ASAT, ALAT, alkaline phosphatase, phosphate, total protein, albumin, sodium, potassium, calcium and chloride)
- Serum or urine pregnancy test for WOCBP within 72 hours prior to randomization.
- Gadolinium-enhanced MRI of the brain within 2 weeks prior to randomization. For operated patients, the post-surgery MRI within 48 hours is mandatory and can be used as baseline. However, if a subject is not randomized within 2 weeks from the post-surgery MRI, then a new MRI scan is required and will be used as baseline.
- Demonstrated EGFR gene amplification by centralized testing using EGFR FISH developed by Abbott Molecular.
- Although not considered necessary activities prior to randomization, the following samples are optional and all subjects randomized may consent to participate in future translational research:
 - Tumor tissue remaining following EGFR amplification testing for future TR projects (optional samples, see section [11.8](#))
 - Whole blood for germline DNA and TR projects (optional samples, see section [11.8](#))

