10.4 Study design

Patients are eligible for the quality of life assessment in this study if they fulfill the eligibility criteria (Chapter 3). Should the HRQoL forms not be available in the required language or should the patient refuse to fill out the form, then this should not exclude the patient from further participation in the study. Patients will be informed in the patient informed consent form that they will have their quality of life assessed regularly while involved in this trial. In this phase II trial, HRQoL will be an exploratory outcome and evaluated in a longitudinal design in all patients entered in this study.

HRQoL questionnaires must be filled out at the hospital when patients come for a scheduled visit according to the EORTC “Guidelines for administration of questionnaires” (see Appendix G). The pre-treatment questionnaires must be filled within 2 weeks before randomization. Subsequent questionnaires are administered at week 8 and 16 on-treatment, coinciding with the imaging visits. All patients are requested to complete a HRQoL assessment 6 months after randomization.

Master copies of the HRQoL questionnaires will be sent to the institutions. Additional copies or translations can be provided upon request via the EORTC contact person. The clinical report forms will include a question whether the HRQoL forms have been filled in, and if not, the reason why. The questionnaire will be handed out to the patients by the investigator or a study nurse prior to seeing the doctor for clinical evaluations. The patient should complete the questionnaires by her/himself in her/his own language during the visit as completely and accurately as possible. It is recommended that a key person (e.g. research nurse) at each center should be responsible for questionnaire data collection in order to optimize the compliance of the patient and to ensure the completeness of the data.

The time windows for eligible HRQoL assessments will be as follows:

Assessment	Time window
Baseline	For all patients. Can be completed before or on the day of randomization itself but no earlier than 2 weeks before.
Week 8 (on-treatment)	To be completed at the week 8 MRI visit while on protocol treatment.
Week 16 (on-treatment)	To be completed at the week 16 MRI visit while on protocol treatment.
At 6 months	For all patients. Can be completed at any time during the sixth and seventh month after date of randomization regardless of treatment or progression status.

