	Before Registration	Registration	Baseline 2 Weeks Prior to Randomization	Randomization	During Protocol Treatment, Each Cycle			Every 8 Weeks	EoT ⁹	6 Months After Randomization	Follow-Up
					Day 1 ⁰	Day 14 Arm 1 & 2	Day 21 Arm 1 and 3B and 3A				
PIS/IC for registration (EGFR)	X										Every 12 Weeks
Histology	X		X								
WHO Performance Status			X		X		X				X
Biological samples for central EGFR assessment	X										
EGFR gene amplification			X								
Biological samples for TR projects (optional)			X								
PIS/IC for study			X								
Weight			X		X						
Medical his. & Demographic			X								
Whole blood for germline DNA and TR projects (optional)			X								
Prior anti-cancer therapies			X								
Physical examination ¹			X		X		X				X
Vital signs			X		X		X				X ¹⁰

Table 1. Study Activities (Continued)

	Before Registration	Registration	Baseline 2 Weeks Prior to Randomization	Randomization	During Protocol Treatment, Each Cycle			Every 8 Weeks X ⁸	EoT ⁹	6 Months After Randomization	Follow-Up
					Day 1 ⁰	Day 14 Arm 1 & 2	Day 21 Arm 1 and 3B and 3A				
Quality of life assessment			X						X	Every 12 Weeks	
ECG			X							X ¹⁰	
Concomitant medication collection			X					X			
Steroid intake			X					X		X	
Prophylactic eye drops ¹⁵					X						
Adverse events (CTCAE v.4.0)			X		X			X		X ¹¹	
Hematology ²			X		X	X ⁷					
Biochemistry ³			X		X						
Serum/urine pregnancy test			X ⁴								
Pk samples					X ⁶			X			
PD samples					X ¹²						
PG samples (optional)					X ¹³						
Gd-MRI			X				X				
Survival and further anti-cancer treatments										X	

Table 1. Study Activities (Continued)

- 0 For Day 1 of Cycle 1, if the evaluations listed here have been already performed during the screening phase and within 2 weeks prior to this Day 1, the same results can be used for Cycle 1 and tests do not need to be repeated: physical examination including, but not limited to, WHO performance status and neurological evaluation; ocular examination if clinically indicated; hematology and biochemistry; vital signs; weight.
- 1 Physical examination including neurological evaluation, and ocular examination at baseline and if clinically indicated.
- 2 Including WBC, absolute neutrophil count, lymphocytes, hematocrit, hemoglobin and platelet count.
- 3 Including serum creatinine, total bilirubin, ASAT, ALAT, alkaline phosphatase, phosphate, total protein, albumin, sodium, potassium, calcium and chloride.
- 4 Pregnancy test must be done within 72 hours prior to randomization.

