* Item range is the difference between the possible maximum and the minimum responses to individual items; most items take values from 1 to 4, giving range = 3.

Table 5. Scoring the QLQ-BN20

QLQ-BN20	Item (Question) Numbers	Item Range
Symptom scales		
Future uncertainty (FU)	1, 2, 3, 5	3
Visual disorder (VD)	6, 7, 8	3
Motor dysfunction (MD)	10, 15, 19	3
Communication deficit (CD)	11, 12, 13	3
Headaches (H)	4	3
Seizures (S)	9	3
Drowsiness (Dr)	14	3
Hair loss (HL)	16	3
Itchy skin (IS)	17	3
Weakness of legs (WL)	18	3
Bladder control (BC)	20	3

The brain cancer module (QLQ-BN20) is meant for use among brain cancer subjects varying in disease stage and treatment modality (i.e., surgery, chemotherapy, radiotherapy, etc.). It is meant to be complemented by the QLQ-C30. It is composed of 20 items forming 11 symptom scales (7 single item scales and 4 multi-item scales).

All scales and single items are reported on categorical responses, and will be linearly converted to numeric values 0 through 100. Given a scale, the raw score (RS) is computed as the mean of component items over the number of items answered for that scale. Then the scale score (SS) will be computed as following.

For global health status/QoL, and symptom scales/items,

$$SS = \{(RS - 1) / \text{range}\} \times 100.$$

For Functional scales,

$$SS = \{1 - (RS - 1) / \text{range}\} \times 100.$$

If 50% or more of the items are answered for a given scale, the scale score will be computed as described above. If not, the scale score will not be computed. For example, physical functioning contains 5 items (questions 1 through 5), and the scale score is calculated if at least 3 of the items are answered. For single-item measures (dyspnea, insomnia, appetite loss, constipation, diarrhea, and financial difficulties), none of the single-item measures can be computed if not answered. If a scale score cannot be computed, the outcome for that score is left blank.

Global health status/QoL is the primary HRQoL endpoint. The other scales from the QLQ-C30 and QLQ-BN20 will be analyzed on an exploratory basis as secondary HRQoL endpoints. The financial difficulties scale (QLQ-C30) will not be analyzed.

All QoL analyses will be performed for the subset of the ITT population for whom at least one valid post-baseline QoL form has been collected. A subject will not be included in a change from baseline analysis unless a corresponding valid QoL form at baseline has also been collected.

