Compliance for a group of subjects at a certain time point T is defined as:

$$\text{Compliance (T)} = \frac{\text{Valid QoL form within [L, U]}}{\text{QoL form expected at T}}$$

Where L and U are the lower and upper bound of the time windows associated with T. The protocol schedule as specified in the protocol can be applied to this definition. The resulting values for T, L and U are summarized in [Table 6](#).

Table 6. Visit Window for QoL

	T	L	U	Window Length
Baseline	Date of randomization = D0	D0 – 1 week	D0	1 week
Week 8 (on-treatment)	Week 8 MRI visit date = D1	D1 – 1 week	D1 + 1 week	2 weeks
Week 16 (on-treatment)	Week 16 MRI visit date = D2	D2 – 1 week	D2 + 1 week	2 weeks
At 6 months	D0 + 6 months = D3	D3 – 30 days	D3 + 30 days	2 months

QoL forms are considered as invalid if either:

- All questions on the form are blank.
- The completion date is unknown or it cannot be assigned to a single assessment time point.
- The completion date falls outside all time windows.
- Multiple forms are received during the same time window. In the latter case, the form closest to the intended assessment time will be kept. In case of equidistance, the earlier form will be kept.

Forms are expected at T for each subject that was within the assessment window. A subject is considered to be within the assessment time window if at least one of the following conditions is met:

- At least one valid QoL form received within L and U
- Time on study > time from randomization till T

For the baseline assessment, all subjects are expected to have a completed QoL form.

The compliance rate between the arms will be compared at each post-baseline time point using a chi-square test. The following analyses will be presented per time-point:

- Compliance rate with QoL assessment by treatment group and overall
- Percentage of questions answered by treatment group (summary statistics)

- Comparison of compliance rates (chi-square test or fisher exact test (if expected cell frequencies are < 10))

In case significant differences are found, explanation of these differences should be sought and the analysis strategy adapted accordingly.

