For each scale, the treatment group differences will be evaluated by analyzing the change from baseline to each of the three post-baseline time-points and to the final measurement (last QoL assessment per subject) using a one-way analysis of variance (ANOVA) model. Simple summary statistics for QoL assessments at each timepoint will also be presented. No adjustment for multiplicity is made since it is exploratory. For QoL assessment data, AbbVie will only perform and present simple summary statistics at each timepoint and change from baseline analysis. Other QoL data will be modeled and analyzed by EORTC.

Changes in HRQoL scores per time point will be evaluated by classifying them according to the 10 point change threshold into 3 categories:

- **Improved:** defined as a 10 point or more improvement (i.e., increase for functional scales and decrease for symptom scales) from baseline.
- **Stable:** defined as a less than 10 point change from baseline.
- **Deteriorated:** defined as a 10 point or more deterioration (i.e., decrease for functional scales and increase for symptom scales) from baseline. Subjects without a valid HRQoL outcome will be considered as having deteriorated.

In case of discrete numbers ($N < 10$), categories may be combined. The subsequent proportions will be compared between treatment arms using a chi-square test in the intent-to-treat population.

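### SAP Table 6 invalidates baseline quality-of-life forms that the protocol allows, and SAP 10.3 leaves the population of the three-category analysis unsettled

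*SAP*

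**What the plan says.** **Baseline window.** Protocol 10.4 says of the baseline questionnaire: "Can be completed before or on the day of randomization itself but no earlier than 2 weeks before". Protocol 6.2 sets the same limit for the whole baseline work-up: "All pretreatment evaluations should be performed within 2 weeks before randomization". In the SAP, the Table 1 column that carries the baseline QoL assessment is headed "Baseline 2 Weeks Prior to Randomization". SAP Table 6 (Section 10.3) nevertheless runs the baseline window from one week before randomization (D0) to D0, with a stated length of 1 week. The SAP introduces that table with "The protocol schedule as specified in the protocol can be applied to this definition". Among its grounds for declaring a form invalid is "The completion date falls outside all time windows". It then adds: "A subject will not be included in a change from baseline analysis unless a corresponding valid QoL form at baseline has also been collected".

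**Population.** SAP 10.3 says all QoL analyses will be done "for the subset of the ITT population for whom at least one valid post-baseline QoL form has been collected". Later in the same section, for the improved/stable/deteriorated classification, it says "Subjects without a valid HRQoL outcome will be considered as having deteriorated", and it places the chi-square comparison in the intent-to-treat population. Protocol 10.5 has the same two rules for that classification.

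**Status.** Protocol 10.2 makes HRQoL exploratory. Global health status is the primary HRQoL scale, and a 10-point change is taken as clinically relevant.

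**The concern.** The main HRQoL outcome is a change from baseline, so a patient without a valid baseline form contributes nothing to it. Under Table 6, a site that followed the protocol and collected the form on day -10, for example, has collected an invalid form. The data exist and were gathered on schedule, but the analysis rule discards them.

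The second problem concerns patients who have no post-baseline form at all. One SAP sentence removes them from every QoL analysis. Another counts them as deteriorated in an ITT comparison. Week 8 and week 16 forms are collected only on protocol treatment, and treatment stops at progression, so this group should be larger in the control arm if the design assumptions are right. If the choice between the two rules is left open until the data are seen, it can decide whether the arms appear to differ.

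**Working it through.** **1. The plan's own HRQoL sample size.** Inputs from Protocol 10.5: difference 10 points, SD 20, two-sided alpha 5%, power 80%.

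- Normal approximation: n per arm = 2 × (1.96 + 0.842)² × (20/10)² = 62.8, so 63.
- t-test: 63.8, so 64.

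The stated 64 per arm (128 in total) is reproduced.

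**2. Effect of the one-week baseline window.** The trial plans 240 patients at 1:1:1, so 80 per arm. The allowed dates are day -14 to day 0, which is 15 days. Table 6 accepts day -7 to day 0 and rejects day -14 to day -8, which is 7 days. Let f be the share of forms dated in the rejected days. The documents do not give f, so these are assumed values. Valid baselines per arm = 80 × (1 - f). Power for 10 points is shown as if nothing else were missing.

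| f | Valid baselines per arm | Power |
|---|---|---|
| 0 | 80 | 88% |
| 10% | 72 | 85% |
| 20% | 64 | 80-81% |
| 30% | 56 | 75% |
| 47% (7/15, dates uniform) | 42 | 62-63% |

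The stated minimum of 64 is lost once f exceeds 1 - 64/80 = 20%. With uniform dates, 240 × 7/15 = 112 forms in the whole trial would be invalid.

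**3. Patients for whom the two population rules differ.** The subset sentence removes only a patient with no valid post-baseline form at any time point. The earliest such form falls in the week 8 window, which Table 6 opens one week before the week 8 MRI visit, so at about week 7 (49/30.4375 = 1.61 months). Exponential curves are assumed, with the design medians from SAP 4.4: OS 7 vs 12.9 months, PFS 2.6 vs 4.8 months. Share with an event = 1 - 2^(-1.61/median).

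- Dead before week 7: 14.7% control, 8.3% ABT-414. Times 80: about 12 vs 7.
- PFS event before week 7: 34.9% control, 20.7% ABT-414. Times 80: about 28 vs 17.

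The first line is a floor for patients who cannot return any form. The second is a ceiling on loss through early progression or death, because some of these patients will complete the month 6 form, which is due regardless of treatment or progression.

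**4. Does the choice of rule matter?** As an illustration, let the deterioration rate q among patients with a form be the same in both arms (assumption). The subset rule then shows a difference of 0. The ITT rule gives a difference of (1 - q) × (control share without a form - ABT-414 share without a form). The gap between shares is 6.4 points at the floor (14.7 - 8.3) and 14.2 points at the ceiling (34.9 - 20.7).

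- q = 20%: 0.8 × 6.4 to 0.8 × 14.2, so about 5 to 11 points.
- q = 40%: 0.6 × 6.4 to 0.6 × 14.2, so about 4 to 8.5 points.

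The two rules therefore give different answers on the same data.

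**The case against.** **On the window.** The size rests wholly on an assumed date distribution. If sites mostly collect the form in the last week, little is lost: at f = 10% there are still 72 per arm. The SAP was written for protocol version 6, while the supplied protocol is a later text, so the version 6 window cannot be checked. Both points stand as limits on size and certainty. Neither removes the conflict, because the SAP's own Table 1 shows 2 weeks and the SAP presents Table 6 as following from the protocol schedule.

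**On the population.** A coherent reading is available. The specific ITT sentence would govern the three-category test, and the general subset sentence the change scores. SAP 10.3 and Section 12 divide the work in a similar way, with the sponsor presenting only summary statistics and change from baseline. Leaving patients without forms out of a change-score ANOVA contradicts no protocol rule. This has force, but the subset sentence covers all QoL analyses and the SAP nowhere limits it.

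**Stronger readings that the documents do not support.**

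- A reader might infer that the SAP drops early failures and so makes the main HRQoL result wrong. It does not settle that: the SAP keeps the protocol's deteriorated rule and ITT population for the classification. The result is undetermined.
- A reader might infer that a patient with an invalidated baseline is certainly counted as deteriorated. That is one reading. The rule requiring a valid baseline for any change analysis points to exclusion instead.
- A reader might count every PFS event by week 8 (38.8% vs 23.3%, about 31 vs 19 of 80) as lost. The window opens at week 7, and the form is completed at the same MRI visit at which progression may be found.

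**On consequence.** HRQoL is exploratory, Protocol 10.5 stresses the magnitude of differences over comparative tests, and sensitivity analyses for missing forms are planned. This limits the importance of the point.

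**Conclusion.** The baseline window in SAP Table 6 is wrong as written. It contradicts the protocol and SAP Table 1, and the invalid-form rule turns that into loss of compliant data from every change-from-baseline analysis. How much is lost depends on form dates that the documents do not give. The protocol's minimum of 64 per arm fails if more than 20% of forms predate day -7, all else being complete.

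The population question is an internal inconsistency in SAP 10.3. Under exponential curves with the design medians it concerns about 12-28 of 80 control and 7-17 of 80 ABT-414 patients, fewer if progressing patients complete the week 8 or month 6 form. The arms lose patients at different rates, so the choice can change the estimated difference.

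The consequence is confined to an exploratory endpoint. OS, PFS, ORR and the type I error strategy are not affected.

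**What to change.** 1. SAP Table 6, baseline row: set the lower bound to D0 minus 2 weeks and the window length to 2 weeks.
2. SAP 10.3: limit the sentence that restricts analyses to patients with a valid post-baseline form to the descriptive and change-score analyses. State that the improved/stable/deteriorated analysis uses all ITT patients, with a missing outcome counted as deteriorated, as in Protocol 10.5.

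Both are wording changes that need no new data and leave the sample size as it is. The one small cost is that some accepted baseline forms will be up to a week older than Table 6 now permits.
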